7.1. Demographics

The continuous demographic variables, age (year), weight (kg), height (cm), Body Mass Index (BMI) (kg/m^2) and Body Surface Area (BSA) (m^2) will be summarized using descriptive statistics (e.g. n, mean, standard deviation, median, minimum, and maximum) by treatment arm, dose cohort and overall. BMI category ($<25 \text{ kg}/\text{m}^2$, $\geq 25 \text{ kg}/\text{m}^2$, Missing) will be summarized with frequency counts.

Age is calculated based on the date of birth and the date of informed consent. In the case date of birth is missing or partial, age collected in the Case Report Form (CRF) will be used. Age category (≤ 70 , > 70) will be summarized with frequency counts.

BSA (m^2) is calculated as follows:

$$\left(\frac{\text{Height (cm)} \times \text{Weight (kg)}}{3600} \right)^{1/2} \text{ (based on the Mosteller formula).}$$

BMI is calculated as follows:

$$\left(\frac{\text{Weight (kg)}}{(\text{Height (m)})^2} \right)$$

[figure not shown]
Race, sex and ethnicity will be summarized with frequency tabulations by treatment arm, dose cohort and overall.

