17.2.1. Calculation Using Dates

Calculations using dates (e.g., subject's age or relative day after the first dose of any study drug) will adhere to the following conventions.

Study days after the start day of study drug (referred as DSTART) will be calculated as the difference between the date of interest and the first date of dosing of study drug plus 1 day. The generalized calculation algorithm for relative day is the following:

If TARGET DATE \geq DSTART then STUDY DAY = (TARGET DATE – DSTART) + 1;

Else use STUDY DAY = TARGET DATE – DSTART.

Note that Study Day 1 is the first day of treatment of study drug (i.e. the earliest date between CC-122, ibrutinib and obinutuzumab). Negative study days are reflective of observations obtained during the baseline/screening period. Note: Partial dates for the first study drug are not imputed in general. All effort should be made to avoid incomplete study drug start dates.

Age (expressed in days) is calculated: AGE = CONSENT – DATE of BIRTH + 1. In practice, age will be transformed into years by dividing the difference by 365.25 days, then truncating. Preference is for using calculated age from clinical database. When not available, calculated age from CRF or Interactive Voice Response System (IVRS) may be used.

Partial birth date: impute missing day as 15th of the month; impute missing month as July; set missing age for missing year.

Intervals that are presented in weeks will be transformed from days to weeks by using (without truncation) the following conversion formula: WEEKS = DAYS / 7

Intervals that are presented in months will be transformed from days to months by using (without truncation) the following conversion formula: MONTHS = DAYS / 30.4375

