17.4. Date Imputation Guideline

This subsection gives guideline on imputation of complete or partial missing AEs, or Concomitant medications start and/or stop dates.

Incomplete Start Date:

Missing day and month

- If the year is the same as the year of the first dosing date, then the day and month of the first dosing date will be assigned to the missing fields.
- If the year is prior to the year of first dosing date, then December 31 will be assigned to the missing fields.
- If the year is after the year of first dosing, then January 1 will be assigned to the missing fields.

Missing day only

- If the month and year are the same as the year and month of first dosing date, then the first dosing date will be assigned to the missing day.
- If either the year of the partial date is before the year of the first dosing date or the years of the partial date and the first dosing date are the same but the month of partial date is before the month of the first dosing date, then the last day of the month will be assigned to the missing day.
- If either the year of the partial date is after the year of the first dosing date or the years of the partial date and the first dose date are the same but the month of partial date is after the month of the first dosing date, then the first day of the month will be assigned to the missing day.
- If the stop date is not missing, and the imputed start date is after the stop date, the start date will be imputed by the stop date.

Missing day, month, and year

- No imputation is needed, the corresponding AE will be included as TEAE.

Incomplete Stop Date: If the imputed stop date is before the start date, then the imputed stop date will be equal to the start date.

Missing day and month

- If the year of the incomplete stop date is the same as the year of the last dosing date, then the day and month of the last dosing date will be assigned to the missing fields.
- If the year of the incomplete stop date is prior to the year of the last dosing date or prior to the year of the first dosing date, then December 31 will be assigned to the missing fields.
- If the year of the incomplete stop date is prior to the year of the last dosing date but is the same as the year of the first dosing date, then the first dosing date will be assigned to the missing date.
- If the year of the incomplete stop date is after the year of the last dosing date, then January 1 will be assigned to the missing fields.

Missing day only

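### SAP 17.4 gives some year-only stop dates two imputed values and can count an adverse event that ended before dosing as treatment-emergent; partial birth dates also have two rules

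*SAP*

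**What the plan says.** **Stop dates (SAP 17.4, day and month missing).** The second bullet covers years before the last-dosing year, "or prior to the year of the first dosing date, then December 31 will be assigned to the missing fields". The third bullet covers a stop date whose year "is prior to the year of the last dosing date but is the same as the year of the first dosing date", and assigns the first dosing date. A line above both moves any imputed stop that precedes the start to the start date.

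**Start dates (SAP 17.4).** With day and month missing: "If the year is the same as the year of the first dosing date, then the day and month of the first dosing date" fill the gap. If a start is imputed after a known stop, "the start date will be imputed by the stop date", but this correction is printed only as the last bullet of the block for starts missing the day alone. For a start missing altogether: "No imputation is needed, the corresponding AE will be included as TEAE".

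**Definitions that use these dates.** SAP 11.1.1 counts an adverse event (AE) as treatment-emergent if it begins or worsens from the start of any study drug until 28 days after the last dose. Protocol 6.1.2 collects AEs from consent, and Protocol 4.2 allows up to 28 days between consent and first dose.

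**Birth dates.** SAP 7.1: "In the case date of birth is missing or partial, age collected in the Case Report Form (CRF) will be used". SAP 17.2.1, for a partial birth date: "impute missing day as 15th of the month; impute missing month as July".

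**The concern.** An imputation rule should give each partial record one value, and that value should not contradict what was recorded. SAP 17.4 fails the first test for one class of stop dates and the second for one class of AEs.

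The stop-date overlap leaves the imputed stop of an AE or a medication to the programmer's choice of bullet. It may also affect whether a medication begun before dosing counts as concomitant. The start-date gap matters more for interpretation: an AE whose recorded stop shows that it was over before first dose can be tabulated as treatment-emergent, in a trial whose primary endpoint is AE incidence. Because AE tables are by dose cohort, a single record would be visible. The two birth-date rules can put the same subject in different age classes in the subgroup tables of SAP 11.1.3.

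**Working it through.** There is no plan figure to reproduce. The check applies the printed rules literally. The documents give no subject dates, so the example assumes first dose 10 March 2016 and last dose 30 June 2017.

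**1. Stop date with day and month missing**
- Bullet 2 condition: stop year before last-dosing year, or before first-dosing year.
- Bullet 3 condition: stop year before last-dosing year, and equal to first-dosing year.
- The bullet 3 condition is a subset of the bullet 2 condition, so bullet 3 can never apply alone. With first-dosing years 2014 to 2018 and last-dosing years up to 2019, bullet 3 applied in 15 combinations, and bullet 2 applied in all 15.
- Example, stop year 2016: bullet 2 gives 31 December 2016 and bullet 3 gives 10 March 2016, 296 days apart. Depending on the first-dose date, the gap runs from 0 to 365 days.
- If first and last dose fall in the same calendar year, only the first bullet applies and there is no clash. A full course is 24 × 28 = 672 days, so anyone completing it crosses a year end.

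**2. AE that ended before dosing (same first dose)**
- Start 2016 only, stop 1 March 2016: the start becomes 10 March 2016, after the event's own stop date. It counts as a TEAE.
- Start March 2016 with only the day missing, same stop: the start is first set to 10 March, then moved to 1 March by the correction. It is not a TEAE.
- Start 2016 only, stop recorded as February 2016: the stop is imputed to 29 February, which precedes the imputed start of 10 March, so the stop is then reset to 10 March. A pre-dose event becomes a TEAE.
- Start wholly missing, stop 1 March 2016: a TEAE by rule. Extending the correction would not reach this case, because nothing is imputed.

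**3. Size for one misclassified event.** One subject changes the incidence of a preferred term by 1/3 = 33 points in a cohort of 3, 1/6 = 17 points in a cohort of 6, and 1/20 = 5 points in Arm A at its planned 20.

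**4. Birth date.** Assume birth and consent dates uniform over the year. 15 July lies at a fraction m of about 0.536 of the year. Age is off by one when the consent day falls between the true and the imputed birthday, with probability [m² + (1 − m)²]/2 = (0.536² + 0.464²)/2 ≈ 0.25 for year-only birth dates. With only the day missing, it is about 0.25/12 ≈ 2%. The error changes the age class (≤70 or >70) only between ages 70 and 71.

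**The case against.** - **The overlap has a natural reading.** The third bullet is narrower and is phrased as a qualification, so it may be meant as an exception to the second; otherwise it would have no function. That is fair as to intent. But the SAP does not say so, and the second bullet carries no exclusion. Read as an exception, it also gives poor values: an event that began later in that year gets a stop before its start and is reset to a one-day duration.
- **The start-date correction is worded generally.** Only its position confines it to starts missing the day, and the layout here comes from extracted text. If it covers all partial starts, the year-only case with a complete stop closes. The wholly missing start remains open, and for a partial stop the two corrections pull in opposite directions with no stated order.
- **Unknown onset counted as treatment-emergent is conventional and conservative.** Agreed. The fault is only in ignoring a recorded stop that shows the event ended before dosing.
- **Qualifying records should be rare.** They must begin and end between consent and first dose, at most 28 days, yet lack the start month. SAP 17.2 expects AE and medication dates to be complete, and listings show them as recorded. This stands, and it limits the size of the point.
- **The age rules are a side issue.** SAP 17.2.1 also allows age from the CRF or the interactive response system when calculated age is unavailable, and the subgroup tables are descriptive, made at an ethics committee's request. This stands too, but the two rules for a partial birth date still differ.

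**Conclusion.** The point holds as a drafting defect of low impact. As printed, SAP 17.4 gives two values for a year-only stop date in the first-dosing year when the last dose is in a later year. It also lets an AE with a recorded pre-dose stop count as treatment-emergent. SAP 7.1 and 17.2.1 disagree on partial birth dates.

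The 17 to 33 points are a worst case. They assume an Arm B or C cohort of 6 or 3, one preferred term, and no other TEAE under that term in the same subject. Safety cohorts may be larger, because subjects can be added or replaced (Protocol 4.1 and 10.3). The documents do not say how many records are affected.

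A reader might infer more than the documents support:
- **That the AE rules contradict each other.** They do not. A correction is missing, and the result conflicts with the TEAE definition.
- **That pre-treatment events are in the TEAE tables.** The rules permit it, but no such record is shown.
- **That medications drop out of the concomitant tables.** A stop on the first dosing date is only borderline under SAP 9 and 9.2. Medications begun after first dose still qualify.
- **That dose decisions are affected.** The safety review committee reviews DLTs as cohorts complete. In Arms B and C the DLT window opens at Cycle 2 Day 1 and Cycle 1 Day 9, after the first-drug date to which such an event would be imputed. In Arm A the window opens on that date, but SAP 11.1.2 requires a DLT to be treatment-related.

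**What to change.** - **Stop dates.** Delete the third bullet for stop dates missing day and month, so that 31 December applies. No cap is needed for these records, because the last dose falls in a later year.
- **Start dates.** Apply the start-after-stop correction to all partial start dates.
- **TEAE status.** State that an AE whose recorded stop, whether a complete date or a month, lies before first dose is not treatment-emergent, including when the start is wholly missing. Make this check on the recorded stop first, then apply the start-after-stop correction, and only then the stop-to-start reset.
- **Age.** Replace the partial birth date line in SAP 17.2.1 with the CRF-age rule of SAP 7.1.

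The cost is a few lines of SAP text and a small programming change before database lock. No new data are needed.

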17.6. Laboratory Data Handling

For absolute and percent values of basophils, eosinophils, lymphocytes, monocytes, and neutrophils, the missing absolute values will be imputed by (corresponding non-missing percent values \times WBC counts), while the missing percent values will be imputed by (corresponding non-missing absolute values \div WBC counts) $\times 100$. If both absolute and percent values are missing, no imputation will be performed.

[figure not shown]
The following data handling rules for laboratory parameters are for data analysis purpose (Tables and Figures). All original data will be presented as is in the data listings.

Table 11: Data Handling Conventions for Laboratory Parameters

Case	Convention	Example Data
values recorded as “<xx”	Set the numerical value to one tenth less in the next digit/decimal point	Immunoglobulin M (Serum) recorded as “<0.20” (g/l), set the numerical value to 0.199
values recorded as “>xx”	Set the numerical value to one tenth more in the next digit/decimal point	Creatinine clearance recorded as “> 60” (ml/min), set the numerical value to 60.1

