17.8. Laboratory Abnormalities Toxicity Grading as Recommended by IWCLL Guidelines

Subjects will be evaluated for laboratory abnormalities as recommended by the IWCLL guidelines for the diagnosis and treatment of chronic lymphocytic leukemia [REDACTED] as listed below:

Table 13: Grading Scale for Hematologic Toxicity in Chronic Lymphocytic Leukemia Studies

Grade ^[a]	Decrease in Platelets ^[b] or HGB ^[c] (nadir) From Pre-treatment Value (%)	Absolute Neutrophil Count ^[d] (mm ³) (nadir)
0	No change to 10%	≥ 2,000
1	11% - 24%	≥ 1,500 and < 2,000
2	25% - 49%	≥ 1,000 and < 1,500
3	50% - 74%	≥ 500 and < 1,000
4	≥ 75%	< 500

Notes:

^[a]Grades: 1, mild; 2, moderate; 3, severe; 4, life-threatening; 5, fatal. Death occurring as a result of toxicity at any level of decrease from pre-treatment will be recorded as Grade 5.

^[b]Platelet counts must be below normal levels for Grades 1-4. If, at any level of decrease the platelet count is < 20,000/mm³, this will be considered Grade 4 toxicity, unless a severe or life-threatening decrease in the initial platelet count (e.g., 20,000/ mm³) was present pre-treatment, in which case the subject is not evaluable for toxicity referable to platelet counts.

^[c]Hemoglobin (HGB) levels must be below normal levels for Grades 1-4. Baseline and subsequent HGB determinations must be performed before any given transfusions. The use of erythropoietin is irrelevant for the grading of toxicity but should be documented.

^[d]If the absolute neutrophil count (ANC) reaches less than 1,000/ mm³, it should be judged to be Grade 3 toxicity. Other decreases in white blood cell count, or in circulating granulocytes, are not to be considered, since a decrease in white blood cell count is a desired therapeutic end point. A gradual decrease in granulocytes is not a reliable index in CLL for stepwise grading of toxicity. The use of granulocyte colony-stimulating factor (G-CSF) is irrelevant for the grading toxicity but should be documented.

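### SAP 17.6 leaves out a division by 100 when it imputes a missing absolute differential count, so an imputed count is 100 times too high if the formula is programmed literally

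*SAP*

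**What the plan says.** SAP Section 17.6 sets one imputation rule for five cell types: "For absolute and percent values of basophils, eosinophils, lymphocytes, monocytes, and neutrophils". It has two halves.

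- If the absolute count is missing: "the missing absolute values will be imputed by (corresponding non-missing percent values" × WBC count. The bracket closes there, and no further factor follows.
- If the percent is missing: "while the missing percent values will be imputed by (corresponding non-missing absolute values" ÷ WBC count), and the result is then multiplied by 100.

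The rule has one stated limit: "If both absolute and percent values are missing, no imputation will be performed". The section gives no unit for the counts and no storage scale for the percent, and no other section supplies either. It also says that data listings show the original data.

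ANC and ALC are used in several programmed outputs. SAP Section 7.2 summarises and grades both at baseline. Section 11.2 grades laboratory values by CTCAE 4.03 or the IWCLL scale, and plans shift tables, worst-grade counts, summaries by cycle and maximum grade, and plots of ANC percent change from baseline. SAP Table 13 (Section 17.8) gives the IWCLL neutrophil cut-offs; Grade 3, for example, is "≥ 500 and < 1,000" per mm3.

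**The concern.** The two halves of the rule should undo each other, and they do not. The × 100 in the second half means that a percent of ten is held as the number 10. Multiplying 10 by the WBC count then gives a value 100 times the true count.

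For neutrophils the error runs in the unsafe direction. A low ANC becomes a high one, and a derived toxicity grade is lowered or lost. For lymphocytes, an ordinary count reads as gross lymphocytosis. The study's primary objectives concern safety, so the programmed laboratory toxicity tables matter, and a wrong derivation rule would make them disagree with the listings.

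**Working it through.** **Inputs.** The two formulas come from SAP 17.6. The ANC cut-offs come from SAP Table 13: Grade 0 at 2,000/mm3 or more; Grade 1 from 1,500 to below 2,000; Grade 2 from 1,000 to below 1,500; Grade 3 from 500 to below 1,000; Grade 4 below 500. The WBC and percent values below are illustrative assumptions. The plan states no figure to reproduce.

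**Step 1: round trip.** Take WBC 5.0 and ANC 0.5 (both ×10^9/L).
- Percent by the second formula: (0.5 ÷ 5.0) × 100 = 10.
- Absolute by the first formula as written: 10 × 5.0 = 50.
- Absolute with the missing term: (10 ÷ 100) × 5.0 = 0.5, the starting value.

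In general, the first formula applied to the second gives (absolute ÷ WBC × 100) × WBC = 100 × absolute.

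**Step 2: can a different storage scale rescue the rule?** If percent is stored from 0 to 100, the first formula is 100 times too high. If it is stored as a fraction from 0 to 1, the first formula is right but the second is 100 times too high. No single storage scale makes both correct.

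**Step 3: effect on ANC grade (Table 13).**

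| WBC (/mm3) | Neutrophils (%) | True ANC | True grade | ANC as written | Grade as written |
|---|---|---|---|---|---|
| 4,000 | 45 | 1,800 | 1 | 180,000 | 0 |
| 4,000 | 30 | 1,200 | 2 | 120,000 | 0 |
| 3,000 | 25 | 750 | 3 | 75,000 | 0 |
| 2,500 | 16 | 400 | 4 | 40,000 | 0 |
| 2,000 | 1 | 20 | 4 | 2,000 | 0 |
| 2,000 | 0.95 | 19 | 4 | 1,900 | 1 |
| 2,000 | 0.2 | 4 | 4 | 400 | 4 |

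Dividing the cut-offs by 100 shows where grades survive: 2,000 ÷ 100 = 20 and 500 ÷ 100 = 5. A true ANC from 20 to 1,999/mm3 is graded 0. From 5 to below 20 it keeps a grade, but too low a one. Below 5 it stays Grade 4, and a count of zero is unchanged.

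The CTCAE cut-offs are not reproduced in the documents, so the grades here use Table 13 only. The factor of 100 does not depend on the grading scale.

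**Step 4: lymphocytes.** WBC 20,000/µL with 80% lymphocytes is a true ALC of 0.80 × 20,000 = 16,000/µL. As written, 80 × 20,000 = 1,600,000/µL.

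**Step 5: percent-change plots.** Suppose the true ANC x does not change. If only the baseline is imputed, a later measured value shows (x − 100x) ÷ 100x = −99%. If only a later value is imputed, it shows (100x − x) ÷ x = +9,900%.

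**The case against.** The best defence is one of notation. Read as ordinary arithmetic, ten percent of 5.0 is 0.5, and multiplying a ratio by 100 is how it is expressed as a percent. On that reading the two halves agree, and an experienced programmer would probably code them correctly. This stands in part: the harm depends on literal programming. It does not clear the text. A stored value carries no percent sign, the section states no scale, and a derivation rule in a SAP should not depend on the programmer correcting it.

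The reach is also limited. Protocol Section 6.1.8 asks for the absolute differential, normally from the central laboratory, and SAP 17.3 prefers central values. Protocol Section 6 allows local laboratories in places, so gaps are possible, but they may be few. Original values remain in the listings, so an error could be traced.

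A reader might infer more than the documents support:

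- *That all imputed neutropenia disappears.* It does not. A true ANC below 20/mm3 keeps some grade.
- *That response, duration of response or PFS is distorted, because SAP Table 3 has lymphocyte and neutrophil criteria.* SAP 10.1 has the investigator assess response, and nothing describes re-deriving response or progression from imputed counts.
- *That DLTs, or the NTD and MTD, are affected.* Adverse event intensity is graded by the investigator (SAP 11.1.1). Investigators and sponsor review DLTs as the study proceeds, with the safety review committee deciding after each cohort (Protocol 10.7). None of this is stated to use SAP-imputed differentials.
- *That reported tables are already wrong.* SAP Section 2 has the plan signed before database lock, and nothing shows that any table has been produced.

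**Conclusion.** The formula is wrong as written and should be corrected. The error is exactly 100-fold for each non-zero imputed absolute count of neutrophils, lymphocytes, monocytes, eosinophils or basophils. On Table 13 it turns a true ANC of 20 to 1,999/mm3 into Grade 0.

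This rests on two conditions: percent is held on the 0-100 scale, as the companion formula implies, and the rule is programmed literally. It applies only where the absolute value is missing and both percent and WBC are present; the number of such records is not stated, so no effect on any particular result can be claimed. The exposed outputs are the baseline ANC and ALC summaries, the laboratory worst-grade and shift tables, the by-cycle laboratory summaries and the ANC percent-change plots. The primary endpoints and the efficacy endpoints are not shown to be affected.

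**What to change.** In SAP 17.6, restate the first half of the rule as: absolute = (percent ÷ 100) × WBC count, in the unit of the WBC count. State that percent is on the 0-100 scale. Leave the second half as it is.

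Before database lock, check the derivation program in two ways. First, run a round trip on test values: absolute to percent and back should return the starting count. Second, flag any imputed absolute count that exceeds its WBC count. The literal formula does this whenever percent is above 1, since percent × WBC > WBC exactly when percent > 1; a correct one never does for percents up to 100.

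The cost is one term in one sentence and a short programming check. No new data are needed, and no other analysis has to change.
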